## 14.0 RECRUITMENT METHODS

We have planned for a 40-month enrollment period (see **Timeline**) to recruit 360 men into the proposed study (9 participants/month). This enrollment rate is similar to that in our previous

studies in prostate cancer survivors on ADT [38] and of women cancer survivors into a fall prevention study (N=466). Men will be enrolled into 8 waves of 45 men to maintain reasonable class sizes (15 men per class). Our primary recruitment strategy will be through the Oregon State Cancer Registry (OSCaR), which we have used for previous studies. Typically, 50%-80% of potential participants in our prior trials are respondents from OSCaR recruiting efforts. Current records indicate that there are 6112 living prostate cancer survivors who meet our age criteria in the Portland metro area. Based on recent estimates of ADT use, we expect 45% of this pool to be current or past ADT users and of this group we expect ~25% to be ineligible because they have no sign of frailty and/or have a cognitive limitation or medical contraindications to exercise yielding 2062 men. In our prior studies, ~20% of eligible survivors enroll in exercise trials so using this estimate we could expect to enroll up to 412 men, exceeding our target sample using the registry alone. Since prostate cancer disproportionately affects African American men, we also partner with the African American Health Coalition to recruit African American prostate cancer survivors into the trial. We will also recruit by clinician referral through OHSU Hospital (led by Co-I [name]) and OHSU Community Oncology clinics that serve outer Portland area. Physicians have referred up to 15% of enrollees in past exercise studies. We will also use direct community recruitment using newspaper ads, radio, web and presentations at cancer organizations and conferences, which have yielded ~15%-20% of participants in past trials. We may also receive patient information (e.g., name, phone number, e-mail address, mailing address, and minimal eligibility-related cancer history information) for recruitment purposes from various hospital systems such as Tuality Healthcare and Adventist Medical Center as well as from OHSU sources such as OCTRI's Cohort Discovery, Research Data Warehouse, and OHSU's medical records. After obtaining this demographic data, recruitment will occur via letters, e-mails, phone calls, or letters/announcements via MyChart.

This study will use Epic MyChart® to recruit potential participants. Researchers will work with ITG and/or OCTRI to identify potential participants based upon the above eligibility criteria. Researchers will create a Reporting Workbench query in epic based on inclusion and exclusion criteria. Potential participants will be sent a MyChart® recruitment message asking them to participate. There is no risk of duplicate invitations as it is based on MyChart® accounts combined with Epic records and no duplication is possible.

**Ancillary study:** In addition to the recruitment methods listed above, we will reach out to current and past study participants who have given their permission to be contacted about future study opportunities.

## **15.0 INFORMED CONSENT (REQUIRED, UNLESS A WAIVER OR ALTERATION IS APPROVED BY THE IRB)**

Written informed consent will be obtained from all participants. A copy of the consent form and documentation of consent will be maintained in the participant's medical record as well as stored in a study file kept in a locked cabinet in the Knight Cancer Research Building (for paper documents only) or stored on an encrypted and password protected computer drive in the OHSU Knight Cancer Research Building (for electronic consents and scanned PDFs of paper consents). Electronic data, including the electronic consent, will also be stored in a web-accessible REDCap database housed on an OHSU secure server.

Interested and eligible participants will go to OHSU to meet with the study coordinator to sign a consent form. The study coordinator and PI will make themselves available throughout the consent process to answer any questions regarding the study. The study coordinator will ask

the participant to reflect back the details of the study to ensure the participant's understanding. The participant will also be given a copy of the signed consent form to take home and refer to whenever needed. Participants will be told that participation is voluntary and they may discontinue participation at any time and that participation will not affect their usual care.

Re-consent for modified procedures will be done over the phone or via teleconference. Study team members will inform the participants of the modified procedures and note their verbal agreement to continue on the study.

Individuals who have not previously consented will be screened by phone or teleconference using an IRB approved screening script. After initial screening, interested and eligible participants will consent by an electronic consent process setup through OCTRI's REDCap system (See 17.0 for a description of REDCap's Privacy, Confidentiality, and Data Security). A waiver of documentation of consent will be used to waive the need for a legally valid signature, however, an electronic signature and affirmation of consent will be collected in REDCap. Study staff will sign an attestation form in REDCap after the participant consents. Study staff will proceed with following the outline for remote testing procedures, as previously described in section 3.0 Study Design/Methodology.

## **16.0        CHANGES TO PROTOCOL**

Any modification of this protocol must be documented in the form of a protocol revision or amendment signed by the principal investigator and approved by the Knight Cancer Institute and the IRB before the revision or amendment may be implemented. The only circumstance in which the amendment may be initiated without regulatory approval is for a change necessary to eliminate an apparent and immediate hazard to the patient. In that event, the investigator must notify the IRB in writing within 5 working days after the implementation.

## **17.0        PRIVACY, CONFIDENTIALITY, AND DATA SECURITY**

Standard institutional practices will be followed as described in the OHSU Information Security and Research Data Resource Guide ([http://ozone.ohsu.edu/cc/sec/isg/res\\_sec.pdf](http://ozone.ohsu.edu/cc/sec/isg/res_sec.pdf)) to maintain the confidentiality and security of data collected in this study. Study staff will be trained with regard to these procedures.

Paper files will be stored in locked filing cabinets in restricted access offices at OHSU Knight Cancer Research Building.

Electronic data will be stored on an encrypted and password protected computer drive in the OHSU Knight Cancer Research Building.

Electronic data will also be stored in a web-accessible REDCap database housed on an OHSU secure server. Features of REDCap that protect participants' privacy and data security include:

- Physical Security: OCTRI's REDCap software is housed on servers located in ITG's Advanced Computing Center providing locked physical security
- Electronic Security: The REDCap servers are housed behind both the OHSU firewall and a second ACC firewall. All web-based data transmissions are encrypted with industry-standard SSL methods.

• Controlled User Access: REDCap is employs a robust multi-level security system that enables researchers to easily implement "minimum necessary" data access for their research staff, including specification of data fields that are identifiers. This feature includes "single click" ability to provide completely deidentified (removing all identified data fields and shifting dates) for analysis or other purposes. User activities are logged to enable auditing of all data access. Access is integrated with OHSU's network such that users who are also OHSU employees are authenticated against their OHSU network credentials.

• Data Integrity: REDCap is jointly managed in accordance with OHSU Information Security Directives by ACC staff and members of OCTRI's Biomedical Informatics Program, ensuring fidelity of database configuration and back-ups. User activities are logged to enable auditing of all data changes.

Access to data is restricted to study personnel and requires OHSU ID/password authentication.

Upon enrollment, subjects will be assigned a code that will be used instead of their name, medical record number or other personally identifying information. Electronic files for data analysis will contain only the subject code.

Codes will not contain any part of the 18 HIPAA identifiers (initials, DOB, MRN)

The key associating the codes and the subjects personally identifying information will be restricted to the PI and study staff. The key will be kept secure on a restricted OHSU network drive in a limited access folder.

Data will be transferred in files using encryption.

Data released to other investigators will be labeled with only the code.

Data from this study will be banked in a repository for future use as part of this protocol. Access to data is restricted to study personnel.

## **18.0 OHSU IRB REPORTING OF UNANTICIPATED PROBLEMS AND ADVERSE EVENTS**

Reportable New Information (RNI) will be reported to IRB according to the policies, procedures and guidelines posted on the [OHSU IRB web site](#):

- Fatal and life-threatening events will be reported to OHSU IRB within 5 days of notification of the event. All other reportable events will be submitted to OHSU IRB no later than 5 working days of occurrence or notification of the event. Copies of the report documents will be kept in the study regulatory binder.
- Reportable events are submitted through OHSU eIRB and will be reviewed by OHSU Knight Cancer Institute DSMC and IRB.

## **19.0 OHSU KNIGHT CANCER INSTITUTE DATA AND SAFETY MONITORING PLAN**

In addition to complete study and pharmacy files, complete records must be maintained on each patient enrolled on this protocol. OHSU Knight Clinical Research Quality and Administration (CRQA) shared resource is responsible for ensuring that all member investigators and affiliate investigators conduct clinical research studies in compliance with local IRB standards, state laws, FDA regulations (where applicable), Department of Health & Human Services (DHHS) regulations and NIH policies. The Data and Safety Monitoring Committee (DSMC) is responsible for conducting Quality Assurance audits on Knight approved protocols according to the Data and Safety Monitoring Plan, policies and procedures. Locally initiated observational and low risk interventional studies may be audited by an OHSU Knight DSMC audit team any time after enrollment begins. The Quality Assurance audit process provides assurance that the reported data accurately reflects the data in the primary patient record and that regulatory requirements are met.

### **19.1 Monitoring Plan:**

This study represents a moderate risk to study participants because it is a clinical trial involving human subjects. Though physical activity and exercise may be associated with adverse events (e.g. tiredness, muscle soreness, muscular injury, cardiac events, shortness of breath), most such events are associated with inappropriately vigorous exercise, which is not the objective of this study. The study will be wholly overseen by the OHSU NCI-designated Comprehensive Cancer Institute for both safety and compliance to institutional and NCI policies. The PI is responsible for evaluating each adverse event as it occurs and for notifying the OHSU IRB of the occurrence of an adverse event according to IRB protocols. An interim safety review will occur early in the intervention period to determine potential safety concerns before the total sample has been accrued. The interim safety review will be overseen by OHSU Knight Data Safety and Monitoring Committee (DSMC, see details below) and will occur after the first 45 enrolled men (~1/8th of total sample) have completed 3 months of exercise training to assess early for program safety.

Adverse events related or possibly related to exercise sessions (i.e., group exercise classes, prescribed home program exercise, and physical performance measurement appointments) will be graded according to their significance for severe consequences, such as injury or death, using the following grades determined by the OHSU IRB.

Examples of serious adverse events (life-threatening or disabling and requiring medical attention). Serious adverse events that may occur during exercise in this study include death and cardiovascular events, though these are extremely rare in the absence of significant cardiac pathology.

Examples of moderate adverse events (resolve with treatment). Moderate adverse events that may occur during exercise include symptoms, such as shortness of breath and orthostatic intolerance.

Examples of mild adverse events (do not require treatment). Reports of side effects, such as muscle soreness, moderate tiredness while exercising, and similar discomforts are mild adverse events.

Examples of unexpected adverse events that do not include physical harm. Adverse events can also include breaches of confidentiality, emotional harms, or complaints about study procedures or conduct of investigators.

In this study we do not anticipate moderate or serious adverse events. Only moderate and serious adverse events that are related or possibly related to exercise sessions (i.e., group exercise classes, prescribed home program exercise, and physical performance measurement appointments) will be reported on our Adverse Events Log.

A survey (Adverse Events Survey) was created by the study team to be administered monthly during the participants' year long participation in the study. Adverse events reported through this survey may be followed-up by study staff with a phone call, e-mail, or in person in class during the intervention period, when participants self-report that their reporting condition is due to a study-related exercise activity or if more information is needed to determine reportability. Participants will also have the opportunity to report adverse events during exercise class or at physical performance measurement appointments.

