## **1.0 BACKGROUND/ RATIONALE**

Two million prostate cancer survivors are alive in the U.S. and nearly half (45%) will receive androgen deprivation therapy (ADT) to reduce tumor androgen exposure and slow down cancer progression [1-3]. While beneficial for cancer survival, significant treatment-induced side effects from ADT may lead to serious health consequences including falls, frailty, and dysfunction that contribute to morbidity and mortality.[4-9]

Falls, frailty and dysfunction lead to costly injuries, loss of independence and early death among older persons. Falls are associated with 90% of hip, 50% of vertebral, and 100% of wrist fractures [10] and can cause traumatic brain injury, internal organ damage, hospitalization, disability and death [11]. One-third of those who fall will require assistance with activities of daily living and over half (58%) of those requiring help will need it for more than 6 months [12]. A single fall increases the risk of future falls [11] and recurrent falls increase the rates of nursing home admission and mortality and poor quality of life [13, 14] and may be a symptom of frailty and poor physical and mental health status [15, 16]. Frailty is an overall weakened physiological state usually associated with advanced age. Fried proposed a Frailty Phenotype model of 5 criteria to measure frailty and demonstrated that older adults with at least 3 of the 5 frailty criteria were at increased risk of hospitalization, development of disability, falls and early death [17-25]

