### **19.2. Plan for Reporting Adverse Events**

Serious adverse events will be reported immediately to the Principal Investigator (PI), who will immediately notify all other investigators. The PI will file a full written report to the OHSU Institutional Review Board (IRB) within 24 hours of notification of the serious event, as required by the OHSU IRB. Specifically, the following will be reported, in writing: 1) all deaths in study participants, during the intervention period, regardless of cause, 2) all serious adverse events associated with the study procedures

Moderate adverse events will be tabulated by the PI, who will notify members of the research team if trends are identified. If trends are noted, preventive measures will be implemented, such as providing education of participants in the study to emphasize prevention of the adverse event. Moderate adverse events will be included in annual reports to the OHSU IRB.

Mild adverse events will not be formally logged but, participants will receive advice on avoiding such events.

Unexpected adverse events that do not include physical harm, usually having to do with study procedures, will be reported within 10 days to OHSU IRB, using a written report form.

Adverse events will be reported to NIH according to NIH protocols.

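### The adverse event grades do not place fracture, head injury or hospital admission, so such an injury from a study session can be graded moderate and reach the IRB only in the annual report

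*Combined protocol and SAP*

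**What the plan says.** Section 19.1 (Monitoring Plan) covers events linked, or possibly linked, to exercise classes, prescribed home exercise and performance testing. It says that these "will be graded according to their significance for severe consequences, such as injury or death", using grades set by the IRB.

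- **Serious.** The paragraph opens "Examples of serious adverse events (life-threatening or disabling and requiring medical attention". Its illustrations are limited: "Serious adverse events that may occur during exercise in this study include death and cardiovascular events".
- **Moderate.** The paragraph opens "Examples of moderate adverse events (resolve with treatment". Its illustrations are symptoms: "Moderate adverse events that may occur during exercise include symptoms, such as shortness of breath and orthostatic intolerance".

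Section 19.2 ties the route to the grade. Serious events go at once to the principal investigator and the other investigators, and "The PI will file a full written report to the OHSU Institutional Review Board (IRB) within 24 hours of notification of the serious event". For the lower grade, the investigator tabulates events and alerts the team if a trend appears, and "Moderate adverse events will be included in annual reports to the OHSU IRB".

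Section 18.0 sets a further timetable that does not mention these grades. Fatal and life-threatening events are due within 5 days and other reportable events within 5 working days, with review by the DSMC and the IRB. What is reportable is left to policies on the IRB website.

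Section 1.0 says that falls "can cause traumatic brain injury, internal organ damage, hospitalization, disability and death". Section 3.0 (Primary Endpoint: Falls) counts fractures and head injuries among the results that make a fall injurious. Neither passage is linked to the grades in Section 19.1.

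**The concern.** The grade decides who learns of an event and how soon. The general principle in Section 19.1 names injury beside death as a severe consequence, but the serious and moderate grades that follow give no injury as an example and do not mention hospital admission. Two careful people could grade the same treated wrist fracture differently and send it down different routes.

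The population and interventions make this more than a drafting matter. Section 5.0 admits men who have fallen in the past year or who have slow Timed Up and Go or chair-stand times. In Section 3.0, one arm does lunges and step-ups in a weighted vest and another deliberately works near the limits of stability. Exercise sessions are held remotely, with participants at home.

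Section 19.3 contains no safety threshold of its own; the study stops if the IRB says so. Section 19.4 lets the DSMC suspend or terminate a trial. The safeguard is therefore what these bodies are shown, and when. Several in-session fractures could be tabulated with breathlessness, and the trial could report few or no serious events.

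**Working it through.** No calculation in the plan bears on this point, so the check applies the written rules to a test case. Take a participant who falls during a study class, sustains a fracture or concussion or is briefly admitted, is treated, and recovers.

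1. **Is it covered by Section 19.1?** Yes. It arises from an exercise session.
2. **Is it serious?** Only if it is life-threatening or disabling and also needs medical attention. The second condition is met. The first depends on whether someone judges the injury disabling. Admission does not count by itself, and the examples (death, cardiovascular events) do not help.
3. **Is it moderate?** The descriptor is that the event resolves once treated. In the test case it does, so the event fits.
4. **Which grade wins if both fit?** Section 19.1 does not say. The text permits either.
5. **What follows under Section 19.2?** If serious, a written IRB report within 24 hours. If moderate, tabulation by the investigator and the annual IRB report. An event just after one annual report could wait about 12 months for the next.
6. **Does Section 18.0 close the gap?** If the event is reportable under IRB policy, it is due within 5 working days and goes to the DSMC. The protocol does not reproduce that policy, and Section 19.2 expressly assigns moderate events to the annual report. Nothing states which section prevails.
7. **What else would the DSMC see?** Section 19.4 lists serious event reports, unanticipated problem reports and interim analysis reports for its monthly meeting. Moderate events are not named there or in the continuing-review list. Section 19.1 adds one early safety review after the first 45 men have completed 3 months of training. That is 45/360 = 1/8 of the sample, halfway through their 6-month intervention.

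The same sections also differ on deaths. Sections 19.2 and 19.3 give 24 hours for the IRB notice, and Section 18.0 gives 5 days for fatal events.

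| Route | IRB timing | Applies to the test case? |
|---|---|---|
| Section 19.2, serious | 24 hours | Only if judged disabling or life-threatening |
| Section 18.0, reportable | 5 working days | Depends on policy outside the protocol |
| Section 19.2, moderate | Annual | Yes, if graded moderate |

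**The case against.** The strongest reply is that the protocol does not assign these injuries to the moderate grade. Both paragraphs give examples, not closed lists. A fracture or head injury can be disabling and need medical attention, which makes it serious, and the grading principle itself points to injury. The investigator evaluates each event as it occurs. This stands: the text allows either grade, and a reader who infers that it classes fractures as moderate goes further than the words do.

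A reader might also infer that a moderate injury never reaches the DSMC. The documents do not support that. Section 18.0 sends reportable events to the DSMC, Section 19.1 provides the early safety review, and Section 19.4 gives the DSMC all unanticipated problems at continuing review.

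Nor do the documents make fracture the leading harm of the study exercise. Section 1.0 describes what falls do to older people. Section 19.1 lists soreness, muscular injury, cardiac events and other exercise harms, and Section 3.0 calls the risk of injury slight.

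Other handling exists. There is a monthly adverse event survey, moderate events are logged, the Project Director tracks complaints and injuries (Section 10.0), and every reported fall is followed by telephone (Section 3.0). These mean that injuries would be recorded. They do not fix when an injury must be escalated, or by which route.

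Finally, the grades are the IRB's, so the study team may not be free to rewrite them alone. That affects how the change is made, not whether the gap exists.

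**Conclusion.** The concern holds as a gap with a consequence for safety reporting. The serious grade has no admission criterion and neither grade places a traumatic injury. A treated, non-disabling fracture, head injury or hospital-treated injury from a study session can therefore be graded moderate and miss the 24-hour report.

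The size is a difference in timing: 24 hours under one reading, as much as about 12 months under the other, and 5 working days if Section 18.0 applies. How often this would happen cannot be derived from the documents, which give no rate of in-session injury.

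The conclusion assumes that the event is judged related or possibly related to a study session or testing visit, that the investigator does not consider it disabling or life-threatening, and that IRB policy does not already make it reportable sooner. If that policy does, the practical harm shrinks to an unresolved conflict between Sections 18.0, 19.1 and 19.2. The change should be made, but it is a one-paragraph correction and does not call the trial design into question.

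**What to change.** With IRB agreement, amend Section 19.1 and the sections it feeds:

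- Report as serious any event related or possibly related to a study session or testing visit that is life-threatening, is disabling, leads to inpatient admission, or is a fracture or head injury. The need for medical attention should not be enough alone. Simply exchanging the present conjunction for an alternative would make almost every treated event serious and empty the moderate grade.
- State that an event fitting both grades is reported as serious.
- Reconcile Sections 18.0, 19.1 and 19.2 (and 19.3 for deaths), so that each kind of event has one stated route and deadline.
- List in-session injurious falls by arm in DSMC reports. The confirmation call described in Section 3.0 already asks how each fall happened and what injury followed, so little new data collection is needed.

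The cost is about a paragraph of amendment, the IRB's agreement because the grades are its own, a few extra expedited reports, and possibly a higher published count of serious events.
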